5.0 Enrollment/Randomization

In this prospective, clinical trial we will enroll 60 patients set to undergo volar plate fixation for a distal radius fracture and up to 10 patients receiving nonoperative treatment for a distal radius fracture. Operative patients will be stratified into two groups: 30 high-energy fractures of otherwise normal bone (e.g. motor vehicle crash) and 30 low-energy fractures of osteoporotic bone (e.g. fall from a chair or standing height). Patient study eligibility will be determined through a weekly assessment of the electronic clinic schedule, patient medical records, consultation visits, and by Vanderbilt Hand & Upper Extremity surgeons during preoperative/initial treatment clinical visits. If the patient is determined to be eligible for the study the treating physician (attending, resident, or fellow) will explain the study to the patient and ask if they would like to participate.

Physical Consent Form Process:

If the patient agrees they will be asked to review/sign an informed consent document by the treating physician or other key study personnel. During this time the patient will be given the opportunity to ask any questions they may have about the study. If the patient signs the consent form, the investigator or key study personnel will provide them with a copy of the signed form and a study contact number to call if they have any further questions. Consent will take place in the confines of a private area (e.g. clinic room).

REDCap-based Electronic Consent Form:

The patient consent process may be conducted using a Redcap-based electronic consent form. The consent form has been developed in REDCap, a secure, web-based, HIPAA-compliant, data collection platform with a user management system allowing project owners to grant and control varying levels of access to data collection instruments and data (e.g. read only, de-identified data views) for other users. Potential participants may participate in the consent process by: being approached in-person at VUMC and accessing the REDCap survey via iPad or other portable electronic device. During the in-person consent process, patients will be consented by a member of the key study personnel. Patient signatures will be obtained using a typed or written-signature (via stylus/cursor, etc.). Upon completion of the consent, patients will be provided with a copy of their version

of the consent document by printing a pdf copy of the consent form in clinic/hospital or by providing a home address for mailing of a hard copy of the consent.

In addition to the 60 operative and 10 non-operative distal radius fracture patients, we will enroll 40 healthy volunteers who have no history of a fracture. The age and gender of these individuals will be selected to match the demographics of the distal radius fracture patients requiring operative fixation. These individuals will be recruited from the metropolitan Nashville community. The means of advertising will include flyers placed in prominent campus and community locations, VICTR research notifications distribution list and ResearchMatch (Appendix E), and word-of-mouth. A potential subject responding to one of these notifications would call key study personnel. Initial screening will take place over the phone. Key study personnel will explain the study to the volunteer and give them an opportunity to ask any questions they may have. If the subject is still interested and eligible they will be scheduled for an enrollment visit, a DXA scan and an MRI. At the enrollment visit, key study personnel will again explain the study to the study volunteer and ask if they would like to participate. If the study volunteer agrees they will be asked to review/sign an informed consent document. During this time the volunteer will be given another opportunity to ask any questions they may have about the study. If the volunteer signs the consent form, key study personnel will provide them with a copy of the signed form. Consent will take place in the confines of a private area (e.g. meeting room).

6.0 Study Procedures

Arm 1- Patients with a high-energy or fragility fracture requiring operative fixation

Enrollment/Initial Visit- Study patient eligibility will be determined through a weekly assessment of the electronic clinic schedule, patient medical records, consultation visits, and by Vanderbilt Hand & Upper Extremity surgeons during preoperative clinical visits. The aforementioned inclusion/exclusion criteria will be used to determine eligibility. All patients who meet the general inclusion/exclusion criteria for Arm 1 and have elected to undergo routine volar plate fixation for their distal radius fracture will be asked to participate in the study by key study personnel. If the patient agrees to participate they will be asked to review/sign an informed consent document. Patients will also be asked to complete the following surveys: DASH (Disability of Arm, Shoulder, and Hand) and PRWE (Patient Rated Wrist Evaluation). Patients enrolled electronically may have an opportunity to complete the DASH and PRWE surveys online using Redcap.

Operative Visit- Patients will undergo a routine volar plate fixation for their distal radius fracture. Once the patient has been anesthetized and prior to stabilizing the fracture with a volar plate, the patient's arm will be secured and the orthopaedic surgeon will indent the area between the one-third distal radius and the ultradistal (UD) at 10 to 15 locations (~2 mm apart) using the OsteoProbe-RPI. The indent size is approximately ~300 µm in diameter and ~300 µm in depth.

DXA/MRI Visit - Postoperatively, the patient will visit the Vanderbilt Clinical Research Center (CRC) to undergo a DXA scan of their hips, spine, and contralateral radius. In addition, the patients will undergo an MRI of their contralateral radius at the VUIIS Human Imaging Core (which is near the CRC). We will attempt to schedule this MRI on the same day that they have their DXA scan scheduled. All

imaging will be performed within FDA safety guidelines. All female participants of child-bearing potential will be asked to undergo a serum pregnancy test at the CRC prior to the DXA scan.

Postoperative Visit- Patients will be seen postoperatively in the clinic based on standard of care guidelines. This typically corresponds to visits at 8-10 days, 3 weeks, 6 weeks, and 12 weeks, although these are not mandated dates. During these routine postoperative clinic visits the following will be recorded for research purposes: bilateral grip strength (12 week), pinch strength (12 week), and range of motion (6 & 12 weeks) measurements. In addition, patients will also be asked to complete the following surveys: DASH and PWRE (3, 6, & 12 weeks).

Osteoprobe Sterilization

Each probe tip will be new and sterilized. The PMMA block will be disinfected following standard sterilization procedures. All patient bone indentations will be taken using the Osteoprobe and then the PMMA block will be indented. The Osteoprobe will not be used on the patient following indentation of the PMMA block. The RPI instrument will be covered with a sterilized sleeve.

Arm 2- Patients with no fracture (Healthy Volunteers)

Enrollment Visit- The aforementioned inclusion/exclusion criteria will be used to determine eligibility for healthy volunteers. All volunteers who report to Vanderbilt Hand Center to take part in this study will be asked to review/sign an informed consent document. Healthy study participants will also be asked to complete a DASH questionnaire.

DXA/MRI Visit- Healthy study participants will visit the Vanderbilt Clinical Research Center (CRC) to undergo a DXA scan of their hips, spine, and forearm (side chosen at random). In addition, the participants will undergo an MRI of the same forearm scanned by DXA at the VUIIS Human Imaging Core (which is near the CRC). All imaging will be performed within FDA safety guidelines. All female participants of child-bearing potential will be asked to undergo a serum pregnancy test at the CRC prior to the DXA scan.

Arm 3- Patients with a high-energy or fragility fracture requiring non-operative treatment

Enrollment/Initial Visit- Study patient eligibility will be determined through a weekly assessment of the electronic clinic schedule, patient medical records, consultation visits, and by Vanderbilt Hand & Upper Extremity surgeons during initial clinical visits. The aforementioned inclusion/exclusion criteria will be used to determine eligibility. All patients who meet the general inclusion/exclusion criteria for Arm 3 and have elected to undergo nonoperative treatment for their distal radius fracture will be asked to participate in the study by key study personnel. If the patient agrees to participate they will be asked to review/sign an informed consent document. Patients will also be asked to complete the following surveys: DASH (Disability of Arm, Shoulder, and Hand) and PRWE (Patient Rated Wrist Evaluation).

DXA/MRI Visit - Patients will visit the Vanderbilt Clinical Research Center (CRC) to undergo a DXA scan of their hips, spine, and contralateral radius. In addition, the patients may undergo an MRI of their contralateral radius at the VUIIS Human Imaging Core (which is near the CRC). We will attempt to schedule this MRI on the same day that they have their DXA scan scheduled. All imaging will be performed within FDA safety guidelines. All female participants of child-bearing potential will be asked to undergo a serum pregnancy test at the CRC prior to the DXA scan.

Follow-up Visits- Patients will be seen in the clinic based on standard of care guidelines. This typically corresponds to visits at 8-10 days, 1, 2, 3, 4, 6, 8, 12, and 16 weeks post-treatment, although these are not mandated dates. During some of these routine follow-up clinic visits the following will be recorded for research purposes: bilateral grip strength (12 week), pinch strength (12 week), and range of motion (6 & 12 weeks) measurements. In addition, patients will also be asked to complete the following surveys: DASH and PWRE (3, 6, & 12 weeks).

7.0 Risks

Potential Risks:

Infection Risk (Arm 1 only):

As with any surgical procedure there is a slight risk of infection. To minimize this risk, the OsteoProbe-RPI probe tip used to indent bone will be new and sterilized. The PMMA block will be disinfected prior to surgery. All patient bone indentations will be taken using the Osteoprobe and then the PMMA block will be indented. The Osteoprobe will not be used on the patient following indentation of the PMMA block. In addition, a sterilized sleeve will cover all other portions of the OsteoProbe machine that are located in the sterile, surgical field of the operating room. During the routine surgical procedure, the patient will be anesthetized so the use of the OsteoProbe-RPI instrument should not cause any discomfort or pain to the patient. The indent is much smaller than the bone screws that will secure the fracture plate.

Radiation Risks:

All study participants will undergo a DXA scan to measure their areal bone mineral density (aBMD), which will slightly increase their radiation exposure. The amount of radiation they receive from the DXA scan will be equivalent to exposure during a flight from Nashville to Denver or one day of exposure to natural background radiation. Study participants who are pregnant will be excluded from participating in this study due to the DXA scan requirement.

MRI Risks:

Some study participants may be undergoing an MRI to measure pore and bound water. MRIs do not use ionizing radiation so there are no known harmful side-effects associated with temporary exposure to the strong magnetic field used by MRI scanners. However, risks of MRI include:

- Ferromagnetic objects brought into the room will be pulled toward the magnet.
- If a subject has implanted metal or medical devices they may experience abnormal torques or fail to function properly.
- There is a risk of tissue heating if there is excessive power deposition of

- radio-frequency electromagnetic waves.
- There is a risk of peripheral nerve stimulation if gradients are switched too rapidly.
- The subjects may experience a claustrophobic reaction when in the magnet.
- There are loud banging noises with MR imaging that may be uncomfortable.

Breach of Confidentiality Risk:

Because patient data is being collected there is a slight risk of a breach of confidentiality. To reduce this risk, most study data will be maintained in the Vanderbilt REDCap database. Vanderbilt Redcap is a secure, web-based application for building and managing online databases. The data obtained and stored in Redcap will only be accessible by research personnel. All Redcap data will be de-identified prior to statistical analysis. All Osteoprobe measurements taken will be relayed from the Osteoprobe to a laptop which is connected to the instrument during the surgical case. The imported data will be displayed in an excel spreadsheet. This excel spreadsheet will be saved on a key study personnel password-protected computer(s). In addition, some data from the excel spreadsheet will be transferred to the Redcap study database. Any physical study forms (ex. consent documents, screening forms, surveys) will be kept in a locked cabinet in the Vanderbilt Hand & Upper Extremity Center Administrative Offices for 6 years following completion of the study. Following this 6 year period, all physical study forms will be disposed of in shred-it confidentiality bins provided by VUMC, and all Osteoprobe data kept in Excel spreadsheets will be permanently deleted from the key study personnel computer(s)

Inconvenience:

The time and inconvenience of participating in the DXA and MRI scans has been considered in this study. We will make our best effort to schedule the DXA/MRI visits on the same day, and if applicable (fracture patients), on the same day as a routine care visit. Patients will be reimbursed \$50 following completion of their DXA scan, and if applicable, \$50 following completion of their MRI scan.

Potential Benefits:

There is no direct patient benefit to participating in this study. Patients may receive a certain psychological reward knowing that they are contributing to increased medical knowledge about fracture risk testing and potential, new diagnostic tools that may improve anti-fracture therapies in future patient populations.

Importance of the knowledge to be gained:

This proposed study is intended to determine if two new, non-X-ray techniques can discriminate between high-energy fractures of normal bone (trauma-related fracture) and low-energy fragility fractures of osteoporotic bone. By affirming the ability of these new techniques to discriminate differences in bone quality, it will provide justification for larger, prospective studies that can evaluate the ability of these new techniques to predict fracture risk, assess whether these techniques are informative on how drug therapy is affecting bone, and determine whether these techniques are useful in the surgical setting. Such knowledge is important because the current gold-standard for assessing fracture risk does not accurately identify

individuals at of an osteoporotic risk. The potential importance of this knowledge outweighs the minimal risk of harm to study participants.

8.0 Reporting of Adverse Events or Unanticipated Problems involving Risk to Participants or Others

A data and safety monitoring (DSM) team will be formed for this study, which will consist of: Drs. [name] and [name] and other researchers involved in this study. The DSM team will meet every 6 months to review study procedures, recruitment, and adverse events that occur throughout the study. In the event of an adverse event or patient complication, both Drs. [name] and [name] will be notified by key study personnel immediately so they can determine if any changes to the protocol need to be made. The IRB will also be notified of any adverse events that may occur as a result of the patient's participation in this study. If an unexpected issue is identified with one of the study patients, the DSM team will be responsible for determining how to address, mitigate, and/or eliminate such risk from the study. In such cases, the protocol will be terminated, until an appropriate course of action is determined by the research team, in conjunction with the IRB.

9.0 Study Withdrawal/Discontinuation

Participation in this study is voluntary. If at any time a study participant wishes to be withdrawn from the study, they may do so by contacting any of the key study personnel and letting them know they withdraw their consent. The date in which the participant withdraws their consent will be noted in their study file. Any information gathered up to the point of consent withdrawal will still be used for research and reporting.

10.0 Statistical Considerations

Data will be analyzed using the statistical software package Stata (version 11.0, College Station, TX) with the assistance of [name], Biostatistician III. Statistical comparisons will be performed using two-sided tests at the 5% significance level. Mann-Whitney test will assess whether differences in properties between groups are statistically significant. Next, general linear models (GLMs) will be used to determine whether the case explains each property after adjusting for aBMD (or T-score), BMI, and age. Using a robust analysis with GLMs, the data will be bootstrap with 500 replicates. Based on the variance from our cadaver studies and expected mean BMS for 'normal' bone as measured by Farr et al. (32), a sample size of 15 per group will provide 87% power to detect a 11.2% difference between the 2 cases at an α of 0.05. With 60 participants (15 per variable) will allow us to determine whether fracture type significantly explains BMS after adjusting for 3 covariates (aBMD, BMI, age). Note that there will be overlap in the participants between Aim 1 and Aim 2. From our limited imaging studies, we can expect bound and pore water of normal bone to be 22 mol $^1\text{H}/\text{L}$ and 10 mol $^1\text{H}/\text{L}$. A sample size of 10 per group will provide 81% power to detect a 22.8% and 51.8% difference in bound and pore water at an α of 0.05. Note that these changes are typically associated with a significant decrease in bone strength by destructive testing (18, 22). With 20 per group we can include a covariate in the regression models.

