By affirming the ability of these tools to discriminate a fragility (osteoporotic) fracture from high-energy (trauma) fracture, the proposed study will provide justification for large prospective studies that i) evaluate the ability of these techniques to predict fracture, ii) assess whether these techniques are informative on how drug therapy is affecting bone, and iii) whether intra-operative RPI is useful to surgical guidance (e.g., placement of bone screws).

AIM 1: DETERMINE WHETHER INDENTATION RESISTANCE IS DIFFERENT BETWEEN PATIENTS WITH FRAGILITY FRACTURES AND THOSE WITH HIGH ENERGY FRACTURES.

Hypothesis: Local indentation resistance (BMS) of the distal one-third radius is lower for patients with a fragility wrist fracture than healthy patients with a traumatic wrist fracture.

Approach: Men and women (>18 y.o.) undergoing surgery to fix a distal radius fracture involving the metaphysis will be recruited into the study. Exclusion criteria will include known risk factors of pathological fractures (e.g., bone metastasis) and long-term or recent treatment for osteoporosis (e.g., bisphosphonate). In addition to standard-of-care, the orthopaedic surgeon will indent the cortex between the one-third distal radius (10-15 sites separated by 2 mm) and the ultradistal (UD) site with the OsteoProbe prior to stabilizing the fracture with a volar plate. The patient's arm will be secured to prevent rotation of the bone. Postoperatively, the patient's hips, spine, and contra-lateral radius will be imaged by DXA to determine aBMD following standard protocols at the Vanderbilt Clinical Research

Center (CRC). Patients will be stratified into two groups: high-energy fracture (e.g., motor vehicle crash) of *normal bone* and low-energy fracture (e.g., fall from a chair or standing height) of *osteoporotic bone*. We expect BMS to be less for the fragility fractures than for non-osteoporotic fractures. In addition, the lower BMS for the fragility fracture group will be significant when including aBMD, age, and body mass index (BMI) as covariates.

AIM 2: DETERMINE WHETHER BOUND WATER AND PORE WATER ARE DIFFERENT BETWEEN PATIENTS WITH FRAGILITY FRACTURES THAN THOSE WITH HIGH ENERGY FRACTURES.

Hypothesis: Bulk bound and pore water of the distal one-third radius will be lower and higher, respectively, for patients with fragility wrist fractures than healthy patients with a traumatic wrist fracture.

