Approach: Postoperatively, patients in Aim 1 may also have their contralateral arm (distal one-third) imaged by our unique UTE-MRI technique (Philips Achieva 3T scanner) using wrist coil at the VUIIS. By including reference markers in the scan, the average concentration of bound water and pore water (mol ¹H per bone volume) will be quantified for a 14 mm axial segment (0.5 mm in-plane resolution). We will also image age-matched and gender-matched individuals without a history of fractures to the operative fracture patient group. We expect the fragility fracture patients to have significantly less bound water and more pore water than high-energy fracture patients and non-fracture patients, and this difference will be significant after adjusting for aBMD and BMI. In addition, bound water will be less and pore water more for the elderly fragility fracture group than for the elderly non-fracture group (also adjusting for aBMD). A group of non-operative distal radius fracture patients will also be recruited to undergo a DXA scan at the CRC and some of those patients will be asked to undergo an MRI scan at VUIIS.

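### The Aim 1 adjusted model fixes three covariates and leaves out sex, although men and women are pooled and nothing balances sex between the two fracture groups

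*Protocol*

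**What the plan says.** Section 10.0 first compares groups without adjustment: "Mann-Whitney test will assess whether differences in properties between groups are statistically significant". General linear models (GLMs) with 500 bootstrap replicates follow, testing the group effect "after adjusting for aBMD (or T-score), BMI, and age".

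The sizing paragraph counts the covariates: "With 60 participants (15 per variable) will allow us to determine" whether "fracture type significantly explains BMS after adjusting for 3 covariates (aBMD, BMI, age". Section 2.0, Aim 1, expects a lower BMS in the fragility group that "will be significant when including aBMD, age, and body mass index (BMI) as covariates". The same three covariates appear each time.

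Aim 1 recruits both sexes: "Men and women (>18 y.o.) undergoing surgery to fix a distal radius fracture". Section 4.0 states that there is no randomization. Section 5.0 sets 30 high-energy and 30 low-energy operative patients and no sex quota. Gender has one role in the design: the 40 volunteers of Arm 2 are matched on age and gender to the operative fracture patients.

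For Aim 2, Section 2.0 says "this difference will be significant after adjusting for aBMD and BMI", and Section 10.0 says "With 20 per group we can include a covariate in the regression models".

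**The concern.** The adjusted model is the step meant to show that fracture type explains BMS beyond known covariates. The two groups are formed by injury energy and bone status, so their sex mix is whatever the clinic supplies. If that mix differs, and if sex is related to BMS beyond density, BMI and age, the adjusted fracture-type coefficient carries part of a sex effect. It could create a difference or hide one.

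The Arm 2 matching does not help. It aligns volunteers with the operative patients as one pool and leaves the sex mix of the fragility and high-energy groups as it is.

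This is not a detail left for a statistical analysis plan. The protocol counts exactly three covariates and rests its sizing argument on that count. The study is also meant to justify larger prospective studies, so a sex difference read as a fracture-type difference would be carried forward.

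**Working it through.** **1. The plan's own count.** One group term plus three covariates gives 60/(1 + 3) = 15 participants per variable, as stated. The list therefore has no place for sex. With sex it is 60/(1 + 4) = 12.

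**2. SD implied by the power statement.** Section 10.0 gives 15 per group, 87% power, a difference of 11.2% and α = 0.05, but no SD. Solving the two-sample t-test for the standardized difference gives d = 1.168, so SD = 11.2%/1.168 = 9.6% of mean BMS. The cadaver sample was half male and half female. For a sex effect of b within-sex SDs, the within-sex SD is therefore 9.6/√(1 + b²/4): 9.5% at b = 0.3 and 8.6% at b = 1.0.

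**3. Assumed inputs.** The documents give none of these:
- 30 per group and no true fracture-type effect.
- Sex effect of 0.3 to 1.0 within-sex SD.
- Fragility group 1 SD older and 0.5 SD lower in density (aBMD) beyond age and sex.
- Women 0.5 SD lower in aBMD, and aBMD falling 0.3 SD per SD of age.
- BMI unrelated, and no covariate other than sex affecting BMS.

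The model is ordinary least squares on fracture type, age, aBMD and BMI, with and without sex.

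**4. False-positive rate and bias without sex in the model, aBMD gap 0.5 SD.** Each range runs from a sex effect of 0.3 SD to 1.0 SD.

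| Women, fragility vs high-energy | False-positive rate | Bias (within-sex SD) | Bias (% of BMS) |
|---|---|---|---|
| 70% vs 50% | 5-7% | 0.04-0.13 | 0.4-1.1 |
| 80% vs 40% | 6-17% | 0.10-0.34 | 1.0-2.9 |
| 85% vs 35% | 7-25% | 0.13-0.44 | 1.2-3.8 |

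The last column is the bias in SDs times the within-sex SD, for example 0.44 × 8.6% = 3.8%. The planned difference is 11.2%. With sex in the model the rate is about 5% throughout.

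**5. A wider aBMD gap.** The groups are defined as osteoporotic versus normal bone, so a gap above 0.5 SD is plausible. With a 1 SD sex effect and a gap of 1.5 SD, the rates without sex are about 5%, 9% and 14% for the three mixes.

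**6. The opposite direction.** If the sex effect runs against the fracture-type effect (aBMD gap 0.5 SD, same range of sex effects), power for 11.2% is:

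| Women, fragility vs high-energy | Without sex | With sex |
|---|---|---|
| 70% vs 50% | 92-94% | 95-98% |
| 80% vs 40% | 80-92% | 93-97% |
| 85% vs 35% | 71-90% | 91-95% |

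**7. Price of adding sex when it has no effect (aBMD gap 0.5 SD).** The standard error of the fracture-type effect rises about 2%, 7% and 11-12% for the three mixes. Adjusted power for 11.2% goes from 95-96% to 90-95%. With a 1 SD sex effect the standard error changes by -8%, -2% and +3%.

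**The case against.** **No evidence of a sex effect.** Confounding needs both a sex imbalance and a sex effect beyond aBMD, BMI and age, and the protocol documents neither. Its cadaver results cover bone, position and porosity and do not mention sex. The protocol does report lower BMS in type 2 diabetes, which is neither excluded nor a covariate. This stands as a limit on what can be claimed. It does not remove the point: sex must already be known, the design already matches on it elsewhere, and nothing else controls it in this comparison.

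**The larger figures need stacked assumptions.** They take a strong imbalance together with a 1 SD sex effect, which is about 1/1.168 = 86% of the whole planned effect. They also shrink as the aBMD gap widens. This stands, and the range above includes the wider gap. The simulation uses plain least-squares tests where the plan bootstraps. Exact rates would differ somewhat, but resampling does not remove bias from an omitted variable.

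**The remedy is partial.** The Mann-Whitney comparison stays unadjusted whatever is added to the GLM. This also stands.

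**Stronger readings that the documents do not support.** A reader might infer that the Aim 1 result will be biased, or that false positives will reach 40%. The first needs data that the protocol does not give. The second comes from multiplying an assumed residual sex effect by an assumed difference in the share of women, without modelling the covariates. A reader might also take the Arm 2 matching as proof that the sponsor expects a sex effect on BMS. It shows only that gender was thought worth matching on for the volunteer comparison.

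**Neighbouring issues.** The open choice between aBMD and T-score, and the differing Aim 2 covariate counts (three in the GLM sentence, two in Aim 2, one in the last sentence of Section 10.0), are separate points. They add nothing to the case on sex.

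**Conclusion.** The omission is real: a closed list of three covariates, a non-randomized comparison that pools men and women, and no rule that balances sex between the fracture groups. The adjusted Aim 1 effect is open to confounding by sex.

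Its size and direction are unknown. Under the assumptions shown it is negligible to small at 70% vs 50% women. It matters only with a marked imbalance and a large sex effect, and it shrinks when the groups differ widely in aBMD. No magnitude was computed for Aim 2.

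The figure of 15 per variable is correct for the model as written. This is a low-priority, inexpensive improvement to the choice of model, not a mistake in the arithmetic.

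**What to change.** **Aim 1.** Add sex to the GLM, in the Section 10.0 covariate list and in the Aim 1 approach. Change the count from three covariates to four and restate the sizing as 60/5 = 12 participants per variable. Keeping 15 would need 15 × 5 = 75 patients, which the power figures above do not call for.

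**Aim 2.** Section 10.0 foresees only one covariate with 20 per group, so leave sex out of the main model and report a sex-adjusted sensitivity analysis.

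**Cost.** A few sentences, one degree of freedom and no new data, because matching Arm 2 on gender already requires the sex of the operative patients. If sex turns out to have no effect, the standard error is about 2-12% larger. Adjusted power for 11.2% stays at about 90% or more under the assumed structure with a 0.5 SD aBMD gap, above the 87% planned for 15 per group. A wider aBMD gap lowers adjusted power with or without sex in the model, because density and fracture type then overlap more.

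### Bootstrapping the adjusted models with only 500 replicates lets a p-value near 0.05 move with the random seed; the interval form also needs a t reference at this sample size (minor)

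*Protocol*

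**What the plan says.** Section 10.0 (Statistical Considerations) sets the threshold: "Statistical comparisons will be performed using two-sided tests at the 5% significance level". The first comparison is unadjusted: "Mann-Whitney test will assess whether differences in properties between groups are statistically significant". After it, "general linear models (GLMs) will be used to determine whether the case explains each property after adjusting for aBMD (or T-score), BMI, and age". The bootstrap sentence follows directly: "Using a robust analysis with GLMs, the data will be bootstrap with 500 replicates".

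The same section puts 60 participants in the adjusted BMS model with three covariates. Section 5.0 splits the 60 operative patients 30 and 30 by fracture type. For bound and pore water, Section 10.0 says "With 20 per group we can include a covariate in the regression models", which is about 40 people per two-group contrast.

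Section 2.0 expects the group differences to stay significant after adjustment: for aBMD, age and BMI in Aim 1, and for aBMD and BMI in Aim 2.

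The replicate count is therefore fixed in the protocol. The interval type, reference distribution, resampling unit and seed are not stated. Those are commonly left to an analysis plan, and their absence is not criticised here.

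**The concern.** The adjusted case coefficient is what supports the claim that indentation resistance or bone water tells us something that aBMD, BMI and age do not. The Mann-Whitney test cannot support that claim. The adjusted claim is judged at a 5% threshold, so anything that moves the p-value without reflecting the data deserves attention.

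Two features of the plan could do that:

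- A bootstrap SE from 500 resamples is itself a random quantity. Two analysts with the same data and code but different seeds get different p-values.
- With 40 to 60 patients, a bootstrap read against the normal distribution, or as a percentile interval, ignores the small-sample correction that an ordinary regression t interval carries.

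The questions are how large each effect is, and which of them the number 500 causes.

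**Working it through.** **Inputs.** From Section 10.0: B = 500 replicates; two-sided alpha 0.05; n = 60 with group plus three covariates (Aim 1); n = 40 per two-group contrast with one covariate (Aim 2). From Section 5.0: 30 per group in Aim 1. The protocol prints no interval width, coverage or p-value for the bootstrap, so it has no figure of its own to reproduce on this point.

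**Step 1: Monte Carlo error of the SE.** The relative error of a bootstrap SE is approximately 1/sqrt(2(B - 1)).

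- B = 500: 1/sqrt(998) = 0.0317, or 3.2%.
- B = 10,000: 1/sqrt(19,998) = 0.0071, or 0.7%.

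**Step 2: effect on a p-value that would settle at 0.050.** The limiting z is 1.96. The 95% range over seeds is z = 1.96/(1 ± 1.96 × relative error).

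| B | z range | p range |
|---|---|---|
| 500 | 1.846 to 2.090 | 0.037 to 0.065 |
| 5,000 | 1.922 to 1.999 | 0.046 to 0.055 |
| 10,000 | 1.933 to 1.988 | 0.047 to 0.053 |

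For a percentile p-value, the tail proportion has standard error sqrt(0.025 × 0.975/B). At B = 500 this is 0.0070, so p varies by 2 × 1.96 × 0.0070 = ±0.027 around 0.05. At B = 10,000 it varies by ±0.006.

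**Step 3: check by re-seeding.** One simulated data set with n = 60 was bootstrapped under 300 seeds at B = 500, using the bootstrap SE with a normal quantile.

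| Limiting p | 95% range over seeds | Share of seeds below 0.05 |
|---|---|---|
| 0.03 | 0.020 to 0.040 | 100% |
| 0.05 | 0.035 to 0.064 | 57% |
| 0.07 | 0.051 to 0.087 | 2% |
| 0.10 | 0.077 to 0.120 | 0% |

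This agrees with the formula and shows that the affected band is narrow.

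**Step 4: interval width.** The quantile effect can be seen directly. Residual degrees of freedom are 60 - 5 = 55 (Aim 1) and 40 - 3 = 37 (Aim 2 with one covariate). The 97.5% t quantiles are 2.004 and 2.026. Using 1.96 instead shortens the interval by 1 - 1.96/2.004 = 2.2% and 1 - 1.96/2.026 = 3.3%.

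A simulation of the case-resampling bootstrap (B = 500, 1,000 data sets in each of 12 scenarios) gave the full picture. The scenarios were n = 60 with three covariates and n = 40 with three or one; a group shift in the covariates of 0 or 1.5 SD; and normal, skewed or unequal-variance errors. The shifts and error shapes are assumptions, because the protocol gives none.

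| Method | Average coverage | Range |
|---|---|---|
| Ordinary t interval | 94.9% | 93.4 to 96.2 |
| Bootstrap SE, t quantile | 94.5% | 92.9 to 96.1 |
| Bootstrap SE, normal quantile | 93.8% | 92.4 to 95.2 |
| Bootstrap percentile | 93.3% | 91.5 to 94.6 |

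Simulation error is about 0.7 points per scenario and 0.2 on the averages. The ratio of bootstrap SE to model SE averaged 0.99 to 1.01 in every scenario. Normal-quantile and percentile intervals were about 2-5% narrower than the t interval. Average type I error is 100 - 93.8 = 6.2% and 100 - 93.3 = 6.7%, against 5.1% for the t interval.

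**The case against.** **The 500 replicates do not make the error bars too narrow.** A reader might infer that they do. The case against that is sound: too few replicates add noise in both directions, the average bootstrap SE matches the model SE, and more replicates would not widen the interval. The shortfall in Step 4 comes from the quantile, not from B.

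**The protocol does not commit to a normal-quantile or percentile interval.** This also stands. An analysis plan may specify another form, and a t quantile on the same 500-replicate SE recovers most of the coverage. The width point is therefore conditional.

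**The seed argument uses a knife-edge.** This stands in part. With the limiting p placed at 0.050, roughly half of all seeds fall below 0.05 at any replicate count, so the 57% is no measure of harm. What more replicates change is the width of the zone in which the seed can decide: 0.037 to 0.065 shrinks to 0.047 to 0.053.

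**Monte Carlo error is small beside ordinary sampling error of the SE.** With 55 residual degrees of freedom the latter is 1/sqrt(110) = 9.5%, and adding 3.2% in quadrature gives only about 10.0%. That is correct, but sampling error is a cost of the sample size, whereas seed noise can be removed at no cost and makes a result irreproducible from the same data.

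**The consequences are limited.** The Mann-Whitney comparison is unaffected, and Sections 2.0 and 7.0 present the study as groundwork for larger prospective studies. That is why the point is minor.

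**Conclusion.** The point holds as a minor one, in two separate parts.

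1. The stated 500 replicates are too few for a p-value judged at 5%. A limiting p of 0.050 may be reported from about 0.037 to 0.065. This rests on B alone and needs no assumption about the data beyond a normal-based reading of the bootstrap SE; a percentile reading is noisier (±0.027).
2. If a normal quantile or percentile interval is used, intervals are about 2-5% short and type I error averages about 6-7%. This rests on assumed covariate shifts and error shapes, and it varies: single scenarios ran from no visible inflation to 8.5% (percentile, skewed errors, n = 40).

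The documents do not support the stronger conclusions that the adjusted results would be unreliable, or that the bootstrap must be replaced. The SE it delivers is essentially unbiased. Moving to a heteroscedasticity-robust SE, or resampling within fracture group, is a matter of preference.

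**What to change.** In Section 10.0, change 500 to about 10,000 replicates and state that the seed is fixed in advance and recorded. In the same sentence, refer the bootstrap SE to a t distribution with the residual degrees of freedom of the model, or report the ordinary t interval alongside the bootstrap one. The first change deals with seed dependence, and the second with interval width. Neither does the other's work.

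The cost is one revised sentence, about a minute of computing and a slightly wider interval. No patients, visits or measurements change. About 5,000 replicates would give most of the gain (0.046 to 0.055) if computing time were a constraint.
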